14.3.3 Safety Assessments

Adverse Events

The TEAEs are summarized for subjects with at least one TEAE, at least one treatment-emergent adverse reaction, at least one serious TEAE, at least one serious treatment-emergent adverse reaction, at least one TEAE leading to drug withdrawn, at least one treatment-emergent adverse reaction leading to drug withdrawn, at least one hepatic AE and at least one adverse event of special interest (AESI).

The frequency and incidence of TEAEs will be summarized by System Organ Class (SOC) and Preferred Term (PT) by treatment and overall. For this table, SOC is sorted by International order; then within SOC, PT is sorted by descending counts under MT-7117 Total group, then descending counts under Placebo group, then alphabetic order for PTs with the same count.

The AE summaries will be presented for the following:

- TEAEs by SOC and PT
- TEAEs by SOC, PT, and severity
- TEAEs by SOC, PT, and relationship
- Treatment-emergent adverse reactions by SOC and PT
- Treatment-emergent adverse reactions by SOC, PT, and severity
- Serious TEAEs by SOC and PT
- Serious treatment-emergent adverse reactions by SOC and PT
- TEAEs leading to drug withdrawn by SOC and PT
- Treatment-emergent Hepatic AEs by SOC and PT

For each of the summaries will be done at the subject level - multiple occurrences of the same event within a subject will be counted once in the summaries by SOC and PT; multiple occurrences of the same event within a subject will be counted once in the maximum intensity category (severe > moderate > mild) and/or maximum drug relationship category (reasonable possibility, no reasonable possibility). If intensity or relationship is found to be missing the most severe occurrence will be imputed for that particular summary.

All AEs for each subject, including multiple occurrences of the same event, will be listed.

Deaths that occur during the study will be listed in a data listing. The data listings for serious TEAE and TEAE leading to drug withdrawn will be generated as well.

Safety laboratory tests

Lab test values and changes from baseline will be summarized descriptively by treatment and visit.

The lab tables will be generated for each lab categories (Hematology, Coagulation, Biochemistry and Urinalysis).

All laboratory data will be listed with clinically relevant values flagged (L=Lower than lower limit of normal range, H=Higher than upper limit of normal range or A=Abnormal).

The number of subjects with post-baseline assessments $\geq 2 \times$ ULN and $\geq 3 \times$ ULN and so on will be calculated for ALT, AST, GGT, ALP, direct and total bilirubin and summarized by treatment group for each post-baseline visit.

The figure of mean (or median) and standard error value of ALT, AST, total bilirubin and alkaline phosphatase by visit will be plotted.

Vital signs and electrocardiogram data

Vital signs and 12-lead ECG variables and changes from baseline will be descriptively summarized at each visit by treatment group.

The baseline for the vital sign parameters and 12-lead ECG measurements will be the last valid assessment obtained on Day 1 prior to the administration of double-blind treatment period.

For ECGs, number and percentage of subjects meeting the criteria listed below will be presented in tables:

- Baseline Corrected QT interval (QTc) <450 msec and >500 msec at EOT
- Baseline QTc <450 msec and 500 msec \geq QTc > 480 msec at EOT
- Baseline QTc <450 msec and 480 msec \geq QTc > 450 msec at EOT
- Increase from baseline at EOT in QTc > 30 msec
- Increase from baseline at EOT in QTc > 60 msec

These criteria will be applied to both Corrected QT interval using Bazett's formula (QTcB) and Corrected QT interval using Fridericia's formula (QTcF).

Physical examination and Nevi evaluation

Physical examination data will be summarized descriptively (number and percentage of the subjects) in tables by treatment and time point.

Nevi appearance will be summarized descriptively (number and percentage of the subjects) in tables by treatment and analysis visit for subjects' suspicious nevi found.

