6 STATISTICAL CONSIDERATIONS

6.1 Descriptive Statistics

Continuous data will be summarized descriptively using the number in the analysis set (N), the number of observations (n), mean, standard deviation (SD), median, minimum and maximum. Categorical data will be summarized using frequency counts and percentages. The denominator for the percentages will be the total number of subjects in the treatment group and analysis population being presented, unless otherwise specified (e.g. on some occasions, percentages may be calculated out of the total number of subjects with available data at a particular visit and/or time point).

Unless otherwise specified, all data will be summarized by analysis visits and treatment group.

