7.2.3.3 Laboratory Tests

(1) Criteria for pre-defined limit

Liver function:

- ALT $\geq 10 \times \text{ULN}$
- $8 \times \text{ULN} \leq \text{ALT} < 10 \times \text{ULN}$
- $5 \times \text{ULN} \leq \text{ALT} < 8 \times \text{ULN}$
- $3 \times \text{ULN} \leq \text{ALT} < 5 \times \text{ULN}$
- $1 \times \text{ULN} \leq \text{ALT} < 3 \times \text{ULN}$

The above same criteria will be applied to AST.

- Total Bilirubin $\geq 2 \times \text{ULN}$
- $1 \times \text{ULN} \leq \text{Total Bilirubin} < 2 \times \text{ULN}$

7.2.3.4 12-Lead ECG

(1) Criteria for pre-defined limit

12-lead ECG:

- Baseline QTc $< 450 \text{ msec}$ and $> 500 \text{ msec}$ at any post baseline
- Baseline QTc $< 450 \text{ msec}$ and $500 \text{ msec} \geq \text{QTc} > 480 \text{ msec}$ at any post baseline
- Baseline QTc $< 450 \text{ msec}$ and $480 \text{ msec} \geq \text{QTc} > 450 \text{ msec}$ at any post baseline
- Increase from baseline in QTc $> 30 \text{ msec}$, 60msec at any post baseline

The above same criteria will be applied to QTcF and QTcB.

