8.3.3 Vital Signs

Absolute values and change from baseline will be summarized descriptively and shift table of clinically relevant categories (Normal, Abnormal(Not Clinically Significant, Clinically Significant)) from baseline to EOT will be also presented for the following parameters .

- Systolic Blood Pressure (mmHg)
- Diastolic Blood Pressure (mmHg)
- Pulse Rate
- Respiratory Rate
- Body Temperature (°C)
- Body Weight (kg)

8.3.4 12-Lead ECGs

Absolute values and changes from baseline will be descriptively summarized and shift table of clinically relevant categories (Normal, Abnormal(Not Clinically Significant, Clinically Significant)) from baseline to EOT will be also presented for the following parameters.

- Heart Rate (bpm)
- PR (msec)
- RR (msec)
- QRS (msec)
- QT (msec)
- QTcF (msec)
- QTcB (msec)

A summary table of the number and percentage will be provided for subjects who met the 12-lead ECG criteria of QTcF and QTcB for pre-defined limit as numerator.

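### All three absolute QTc rows require a baseline below 450 msec, so subjects starting at 450 or more who newly exceed 480 or 500 msec are left out of the count but stay in the default denominator

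*Protocol*

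**What the plan says.** Protocol 14.3.3 lists five QTc criteria, to be applied to both QTcB and QTcF. Three are absolute: above 500, above 480 up to 500, and above 450 up to 480 msec. Each requires a baseline below 450; the highest reads "Baseline Corrected QT interval (QTc) <450 msec and >500 msec at EOT". The other two are increases with no baseline condition: "Increase from baseline at EOT in QTc > 30 msec" and "Increase from baseline at EOT in QTc > 60 msec".

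SAP 7.2.3.4 repeats the list with the baseline condition intact on all three absolute rows. It replaces the end-of-treatment timing with any post-baseline value and adds: "The above same criteria will be applied to QTcF and QTcB". SAP section 1 says that the SAP overrides the protocol on analysis, so this is the operative version.

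SAP 8.3.4 sets only the numerator of the table, namely subjects meeting the "ECG criteria of QTcF and QTcB for pre-defined limit as numerator". The denominator then comes from SAP 6.1: "The denominator for the percentages will be the total number of subjects in the treatment group and analysis population being presented", unless something else is specified. Nothing else is specified for QTc. The safety populations in SAP 5.2 have no QTc condition.

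**The concern.** The row for values above 500 msec exists to show how many subjects in each arm reached that level on study. A subject who starts at 455 and reaches 505 has newly passed both 480 and 500, yet the baseline condition removes that subject from both rows. Those removed are the subjects who start nearest to the thresholds, while the percentage is still taken over everyone in the arm. The increase rows catch such a subject only if the rise is more than 30 msec.

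The same SAP handles liver safety differently. The ALT, AST and bilirubin limits in SAP 7.2.3.3 carry no baseline condition, and SAP 8.3.2 adds a shift table of the maximum post-baseline value against those limits. QTc has no equivalent.

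**Working it through.** The documents state no figure for this table, so there is nothing to reproduce. The check applies the five rows as written in SAP 7.2.3.4.

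**Inputs.** Baseline b, post-baseline value y. Absolute rows: b < 450 and y > 500; b < 450 and 480 < y ≤ 500; b < 450 and 450 < y ≤ 480. Increase rows: y − b > 30; y − b > 60. About 61 subjects per group (Protocol 8.1).

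**Step 1: where example subjects land.**

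| b (msec) | y (msec) | y − b | Rows entered |
|---|---|---|---|
| 440 | 460 | +20 | >450 to 480 |
| 449 | 501 | +52 | >500; increase >30 |
| 450 | 501 | +51 | increase >30 only |
| 455 | 505 | +50 | increase >30 only |
| 450 | 511 | +61 | increase >30 and >60 only |
| 470 | 501 | +31 | increase >30 only |
| 471 | 501 | +30 | none |
| 480 | 505 | +25 | none |
| 495 | 515 | +20 | none |
| 460 | 490 | +30 | none |

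Across all whole-number pairs with b from 450 to 600 and y from 350 to 700, no pair enters any absolute row.

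**Step 2: who vanishes from the whole table.** A subject with 450 ≤ b ≤ T who newly exceeds a threshold T is in no row when T < y ≤ b + 30. This needs b > T − 30. For T = 500 that means baselines above 470 and up to 500. For T = 480 it means baselines above 450 and up to 480.

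**Step 3: which rows are affected.** Call a case new at T if b ≤ T and y > T.
- T = 450: a subject already above 450 cannot be new, so the condition b < 450 is right except at b = 450 exactly. A change from 450 to 455 is new but is not counted.
- T = 480: baselines of 450 to 480 are wrongly left out.
- T = 500: baselines of 450 to 500 are wrongly left out.

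**Step 4: effect on a percentage (illustration).** With one subject in an arm of 61 who has baseline 450 to 500 and exceeds 500, the row reads 0/61 = 0.0%. Counted regardless of baseline it reads 1/61 = 1.6%.

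The denominator has a separate, smaller effect. Suppose one case is counted from baseline below 450, and m subjects have baseline 450 or more. The plan reports 1/61 = 1.6%; among subjects who could be counted it is 1/(61 − m). The documents do not give m. Assuming 2% to 20% of 61 (m = 1 to 12), the result is 1/60 = 1.7% to 1/49 = 2.0%.

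**The case against.** The best defence is that the rows state their condition openly. They report emergence from a baseline below 450, not prevalence above a threshold, and they apply identically in every arm. That stands as a description. It justifies the >450 to 480 row. It does not justify the other two, where a subject starting at 455 has newly crossed, and it does not explain a denominator that includes subjects who cannot be counted.

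Such subjects also remain visible elsewhere. All safety data are listed (SAP 8.3). SAP 8.3.4 gives descriptive statistics and a shift table. Clinically significant ECG abnormalities become adverse events (Protocol 10.9.3). The increase rows catch 455 to 505. This limits the harm, so a reader should not infer that these subjects are lost from the report. None of these outputs gives a count by arm at a msec threshold, however: the shift table uses normal, abnormal not clinically significant and abnormal clinically significant, which follow the investigator's reading.

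The all-subjects denominator is a default that allows exceptions, and no table shells are available. A denominator of subjects with available data would still include baselines of 450 or more.

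A reader might also infer that every absolute percentage is too low by some fixed share. The documents do not support that. The >450 to 480 row is sound for new crossing of 450, and there is no baseline QTc distribution from which to derive a share. Nor do they show bias between arms.

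**Conclusion.** The point holds for the >480 to 500 and >500 rows. New crossings of 480 from baselines of 450 to 480, and of 500 from baselines of 450 to 500, are not counted there. With a rise of 30 msec or less they appear nowhere in the table. On the >450 to 480 row the only defect is a baseline of exactly 450. Under the SAP 6.1 default, the uncounted subjects still dilute the percentages.

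The size cannot be stated. No baseline QTc distribution is given. The visible eligibility criteria contain no QTc limit, but some criteria are redacted, so an exclusion that would make the matter moot cannot be ruled out. The 0/61 against 1/61 comparison assumes one affected subject in an arm of about 61.

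This is a descriptive safety table. No hypothesis test, power figure or defined adverse event of special interest (these are hepatic, Protocol 12.3) depends on it. The change is worth making because it corrects a reported safety count at very little cost.

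**What to change.** In SAP 7.2.3.4, for QTcF and QTcB:

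1. Add counts of subjects with any post-baseline value above 450, above 480 and above 500 msec, regardless of baseline. Denominator: subjects with at least one post-baseline ECG in the period.
2. Beside each, show the new cases, meaning baseline at or below that same threshold. Denominator: subjects with baseline at or below that threshold and at least one post-baseline ECG. This also settles the baseline of exactly 450.
3. Keep the >30 and >60 msec increase rows.
4. State these denominators in SAP 8.3.4 so that the SAP 6.1 default does not apply. This matters for a second reason: footnote e to SAP Table 1 places the ECG at Visit 11 for subjects who elect the extension and at Visit 7 for those who do not. Some subjects in the double-blind safety population may therefore have no post-baseline ECG in that period.

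The cost is a few SAP lines and extra rows in one table, with no new data. The reported percentages may be slightly less favourable.

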14.3.4 Pharmacokinetic Endpoints

Plasma MT-7117 concentrations will be listed for each subject and scheduled visit and treatment

period with the same precision as provided by the bioanalytical laboratory. PK sample collection times, most recent dosing times, as well as derived actual sampling time relative to the most recent dose will be provided in a listing. The actual sampling time relative to the most recent dose will be calculated in hours and rounded to 2 decimal points. Plots of individual concentration vs actual sampling time will be presented overlaid with treatment in different symbols for each treatment by visit or overlaid with visits.

Population PK analysis will be performed using the plasma concentration of MT-7117 obtained in this study in combination with data obtained from other clinical studies. Population PK analysis results will be reported separately from the Clinical Study Report (CSR).

14.3.5 Exploratory Endpoints

[REDACTED]. The details of the statistical analysis method will be fully described in Primary Week 26 Analysis SAP.

Porphyrin and protoporphyrin levels will be listed and summarized by treatment using descriptive statistics.

15 STUDY MANAGEMENT AND ETHICAL AND REGULATORY REQUIREMENTS

15.1 Good Clinical Practice

The Investigator will ensure that this study is conducted in compliance with the 2013 (Fortaleza, Brazil) revision of the 1964 Declaration of Helsinki. This study will also be conducted in accordance with Good Clinical Practice (GCP) requirements described in the current revision of International Council for Harmonisation of Technical Requirements for Pharmaceuticals for Human Use (ICH) Guidelines. This study will also be carried out in accordance with regional and local legal requirements. Before the first subject is enrolled in the study, all ethical and legal requirements will be met.

15.2 Investigator Responsibilities

15.2.1 Informed Consent

Before undergoing any study-specific procedure, all legally competent subjects must consent in writing to participate. An IRB/IEC approved ICF will be given to each subject.

The process of obtaining the informed consent will be in compliance with all regulatory regulations, ICH requirements, and local laws.

15.2.2 Ethical and Regulatory Approval

The study was conducted in accordance with ethical principles that have their origins in the Declaration of Helsinki and that are consistent with GCP as described in:

- Declaration of Helsinki, concerning medical research in humans (Adopted by the 18th World Medical Association [WMA] General Assembly, Helsinki, Finland, June 1964 and amended by the: 29th WMA General Assembly, Tokyo, Japan, October 1975; 35th WMA General Assembly, Venice, Italy, October 1983; 41st WMA General Assembly, Hong Kong, September 1989; 48th WMA General Assembly, Somerset West, Republic of South Africa, October 1996; 52nd WMA General Assembly, Edinburgh, Scotland, October 2000; 53rd WMA General Assembly, Washington DC, USA, October 2002 (Note of Clarification added); 55th WMA General Assembly, Tokyo, Japan, October 2004 (Note of Clarification added); 59th WMA General Assembly, Seoul, Republic of Korea, October 2008; 64th WMA General Assembly, Fortaleza, Brazil, October 2013).
- ICHE6_R2.
- Code of Federal Regulations (21 CFR).

The Investigator and Sponsor will sign this protocol to confirm agreement to abide by it.

Before any study-related procedure is performed on a subject, all IRB/IEC, regulatory authorities, and local approvals of this protocol will be obtained. While the study is ongoing and at study completion/discontinuation, the Sponsor or Investigator will submit information to the IRB/IEC(s) in accordance with institutional/local regulations, for example:

- Information on SUSARs.
- Periodic reports on the progress of the study.
- Notification of the end of study or early termination.
- Final study summary upon completion or closure.

The Sponsor will ensure that any SUSARs from this study and other studies with this study medication are reported promptly to the regulatory authorities.

If it is necessary to amend the protocol during the study, proper notification will be made to the regulatory authorities and IRB/IECs in the form of a Protocol Modification. Protocol Modification requiring IRB/IEC approval may be implemented only after a copy of the IRB/IEC's approval/favorable opinion letter has been transmitted to the Sponsor and regulatory authority approval has been obtained (if required). Protocol Modifications that are intended to eliminate an apparent immediate hazard to subjects may be implemented before receiving Sponsor, regulatory, and/or IRB/IEC approval. However, in this case, approval must be obtained as soon as possible after implementation.

Any protocol or other deviations that occur during the study will be documented and reported to the Sponsor. Depending on the nature of the deviation, this may be reported to the regulatory authority and the IRB/IEC.

15.2.3 Source Document Requirements and Document Access During the Study

The Investigator must retain a comprehensive and centralized filing system of all study-related documentation (including, but not limited to: essential documents, copies of protocols, eCRFs, source data such as original reports of test results, study medication dispensing logs, correspondence, records of informed consent/assent, and other documents pertaining to the conduct of the study) that is suitable for inspection by the Sponsor and representatives of regulatory authorities.

The Investigator/institution will permit study-related monitoring, audits, IRB/IEC reviews, and regulatory inspections providing direct access to source data/documents.

15.2.4 Study Records Retention

Study-related documentation must be kept for at least 25 years or until notified by the Sponsor. Documents should be stored in such a way that they can be accessed/data retrieved at a later date. Consideration should be given to security and environmental risks.

No study document will be destroyed without prior written agreement between the Sponsor and the Investigator. Should the Investigator wish to assign the study records to another party or move them to another location, written agreement must be obtained from the Sponsor.

15.2.5 Protocol Deviations

The Sponsor does not allow prospective deviations from the protocol. Any significant deviations affecting subject eligibility and/or safety must be reviewed or approved by the

IRB/IEC and regulatory authority, as per applicable requirements. The Investigator is responsible for complying with all protocol requirements, and applicable to laws pertaining to protocol deviations. If a protocol deviation occurs (or is retrospectively identified) after a subject has been enrolled, the Investigator is responsible for notifying their IRB/IEC, regulatory authorities (as applicable), and assigned Clinical Monitor or Sponsor.

Protocol deviations considered to be clinically significant will be escalated to the Sponsor and may include corrective measures.

15.3 Study Monitoring

In accordance with applicable regulations, GCP, and the procedures of the Sponsor or its designees, the Study Monitor will periodically contact the Investigator site, and conduct on-site visits. The extent, nature, and frequency of on-site visits will be based on study complexity, enrollment rate, and data quality at the Investigator site. Through these visits and frequent communications (e.g., letter, email, and telephone), the Study Monitor will verify that the investigation is conducted according to protocol, regulatory, and Sponsor requirements.

The Investigator will allow the Study Monitor direct access to all relevant documents and allocate his/her time and the time of his/her personnel to the Study Monitor to discuss findings and any relevant issues.

In addition to contacts during the study, the Study Monitor will contact the Investigator site personnel before the start of the study to discuss the protocol and data collection procedures.

At study closure, the Study Monitor will conduct all activities as indicated in Section 15.5.

15.4 Quality Assurance and Auditing

Authorized representatives of the Sponsor, IRB/IEC, and/or regulatory authorities may conduct an audit or inspection of this study either during or after completion. In such cases, the Investigator will give the auditor/inspector direct access to all relevant documents and source data and will allocate his/her time and the time of his/her personnel as may be required to discuss findings and any relevant issues.

15.5 End of Study and Site Closure

The end of the study is defined as the last visit for the last subject. Upon completion of the study, or if the study or an Investigator site is prematurely discontinued, the following activities, where applicable, must be conducted by the Study Monitor in conjunction with the Investigator:

- Return of all study data to the Sponsor.
- Completion of data clarifications and/or resolutions.
- Accounting, reconciliation, and final disposition of used and unused study medication.
- Review of Investigator site study records for completeness.

Any unresolved AEs of SAEs will be followed according to Section 12.10.

